- Determine whether tamoxifen-resistance and fulvestrant-sensitivity gene expression signatures are observed in patients with cyclinD1 overexpressing breast cancers.
 - A gene signature that distinguishes cells that are responsive to tamoxifen and those that are resistant to tamoxifen has been established using cell lines in vitro. Similarly, a gene signature of the same cells in response to fulvestrant was also determined. Using these signatures obtained in vitro, we will compare whether the same gene signature characterizes tumors that are resistant or sensitive to tamoxifen and fulvestrant respectively in patients samples using selected gene by nanostring analysis by RNA extraction from paraffin embedded sections.
- Determine whether patient's response to tamoxifen or fulvestrant correlates with the response of their primary cells in vitro.
 - The organoid core facility has recently developed a method by which cells from primary tumors from patients can be grown in vitro. When samples are available for culture in vitro, we will test whether the cells derived from individual patients respond the same as the tumor in vivo in the same patient. For this experiment, cells in culture will be treated with the same drug (tamoxifen or fulvestrant) as the patient has received. We will conduct standard proliferation assays (MTT) assay over a range of doses of the drug as we are aware that intratumoral doses achieved clinically and doses in vitro can be quite different. If successful this analysis would validate the use of such organoid culture to predict patient response in the future. Therefore, we view this analysis as an opportunity to determine proof of principal of such technique and may have wide impact for several studies in the future.

Statistical Analysis Plan

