Robertson et al (2007) gave a mean change from baseline in Ki67 of a 2.8% decline and a standard deviation of 22.5% of cells staining for Ki67 for patients receiving fulvestrant 250 mg. In the placebo group they reported a mean reduction and standard deviation of 7.1% +/- 18.0%. There was no significant difference ($p=0.97$) between groups. In the present study, we hypothesize that for women with cyclin D1 overexpression, high dose fulvestrant will have a higher mean reduction in Ki67 than tamoxifen. 58 patients (29 patients in each study treatment arm) will be required to detect a difference between treatments of 15% in cells staining for Ki67 (mean reduction from baseline of 5% for Ki67 level in the tamoxifen group vs. 20% in the fulvestrant group) with power 0.80 for a two-sided test at the 0.05 level. We estimate that 10% of those enrolled to the tamoxifen arm may dropout from the study; however, since fulvestrant is given as a one-time dose, we do not expect attrition from this arm of the study. To account for drop-outs 32 patients will be randomized to each arm.

Treatment assignment

Comparison in the Change of Proliferation Index between Fulvestrant and Tamoxifen in Cyclin D1 +, Estrogen Receptor + Breast Cancer

[name], PI

Essential Elements

#13, 09/13/2017

A total of 64 patients will be randomized in a 1:1 allocation (32 patients to the tamoxifen arm and 32 to the fulvestrant arm) stratified by menopausal status (pre vs. post).. Randomization will be initiated at Mount Sinai by the research pharmacy, using separate randomization lists for pre and post menopausal patients..

Endpoints

Primary endpoint:

- The change in proliferation index between core biopsy and definitive surgery as measured by the percentage of cells staining for Ki67 in each treatment arm, stratified by menopausal status.

Secondary endpoints:

- Determine whether there is a differential treatment effect between tamoxifen and fulvestrant for pre and post menopausal patients.
- The change in estrogen receptor and progesterone receptor levels between core biopsy and definitive surgery in patients treated with fulvestrant or tamoxifen.
- Determine whether tamoxifen-resistance and fulvestrant-sensitivity gene expression signatures are observed in patients with cyclinD1 overexpressing breast cancers.
- Determine whether patient's response to tamoxifen or fulvestrant correlates with the response of their primary cells in vitro.

Data Analysis:

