An intent to treat analysis will be applied to this study. All primary and secondary analysis will be performed, stratified by menopausal status(pre vs. post). Primary continuous response rate of percentage of cells staining for Ki67 between treatment groups will be analyzed using stratified analysis of covariance (ANCOVA). Treatment groups will be compared by stratified analysis of covariance with respect to the outcome variable of post treatment percentage of cells staining for Ki67 with covariate baseline percentage of cells staining for Ki67, allowing for estimation of the mean change from baseline. Assumptions underlying ANCOVA will be evaluated. Transformation of the data will be undertaken if appropriate. A treatment diary will be used for patients enrolled to the tamoxifen arm to record all treatment doses and to help account for any missing data.

A secondary analysis will be a per protocol analysis. Potential interaction will be tested for treatment by stratum (menopausal status) to determine if there exists a differential treatment effect for pre and post menopausal subjects. The mean change in levels (expressed as a percentage of cells staining positive within the breast tumor) of ER (and PR) between pre-treatment and post-treatment will be compared between treatment arms by ANCOVA stratified by menopausal status as in the statistical analysis of the primary objective.

Gene signatures that distinguish cells that are responsive and those that are resistant to tamoxifen have been established using cell lines in vitro. Gene signatures for responsiveness/resistance to fulvestrant have also been established. Presence of these gene signatures will be determined for all patients in this study. Patients having signatures for responsiveness or resistance to tamoxifen (fulvestrant) will be compared with respect to change in Ki67 after treatment with tamoxifen (fulvestrant) by stratified ANCOVA.

Comparison in the Change of Proliferation Index between Fulvestrant and Tamoxifen in Cyclin D1 +, Estrogen Receptor + Breast Cancer

[name], PI

Essential Elements

#13, 09/13/2017

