Following examination by the study pathologist of the Ki67 immunohistochemically stained sections and an additional section stained with H&E, areas of viable tumor tissue within the cores will be identified, the extent of antibody staining assessed using appropriate protocols for digital image capture and analysis. It is our expectation that the cores will show considerable intratumoral heterogeneity in the extent of staining and that individual strongly staining nuclei may be interspersed among weakly or negatively stained cells. In order to address the problem of intratumoral heterogeneity, we will obtain digital images of the entire tissue section and determine the number of positively stained nuclei per 100,000 μm^2 of viable tumor tissue.

In addition, manual scoring of cyclinD1, STAT3, STAT5 and Ki67 will also be performed. The manual scoring will be performed as described previously where a score for percentage of cells stained and a score for intensity of scoring is obtained and then added to obtain an Allred score.

For the ER, we predict that pre-treatment specimens from both arms will show evidence of ER staining in the nucleus. In post-treatment specimens, the fulvestrant alone arm will show reduced nuclear staining of ER and some cytoplasmic staining of ER. The staining of ER will be assessed with the 6F11 monoclonal antibody (Vision Biosystem) as this is the antibody used clinically at this time. Intensity will be scored (0, 1+, 2+, 3+) by the level of staining in the nucleus and cytoplasm. ER will also be expressed as a percentage (0-100%) of cells staining positive within the breast tumor.

For the PR, we predict that pre-treatment specimens from both arms will show evidence of PR staining in the nucleus. In post-treatment specimens, the fulvestrant alone arm will show reduced staining of PR given the downregulation of the ER by fulvestrant. Intensity will be scored (0, 1+, 2+, 3+). PR will also be expressed as a percentage (0-100%) of cells staining positive within the breast tumor.

Tunel assay will be used to determine the percentage of cells that underwent apoptosis. Paraffin embedded sections will be stained using the apoptosis detection kit TACS-KL Basic (TA100, R&D systems Inc, Minneapolis) according to the manufacturer's protocol. Sections will be counterstained with 0.2% hematoxylin to detect intact nuclei. Our data suggest that more apoptotic cells will be detected in

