Comparison in the Change of Proliferation Index between Fulvestrant and Tamoxifen in Cyclin D1 +, Estrogen Receptor + Breast Cancer

[name], PI

Essential Elements

#13, 09/13/2017

the cyclinD1 overexpressing tumors in response to fulvestrant compared to the tamoxifen. This analysis will therefore allow us to test this possibility in humans. Further, the analysis of the rate of apoptosis will provide an independent readout of the effect of treatments in addition to proliferation measured by Ki67.

For tumors greater than 1 cm, a small portion of the surgical specimen not needed for diagnostics will be divided: half will be frozen for subsequent RNA extraction and expression profiling, and half will be utilized for primary tissue culture.

For RNA extraction and gene expression profiling, a gene signature that distinguishes cells that are responsive to tamoxifen and those that are resistant to tamoxifen has been established using cell lines in vitro. Similarly, a gene signature of the same cells in response to fulvestrant was also determined. Using these signatures obtained in vitro, we will compare whether the same gene signature characterizes tumors that are resistant or sensitive to tamoxifen and fulvestrant respectively in patients samples using selected gene by nanostring analysis by RNA extraction from paraffin embedded sections.

In order to assess response of a patient's primary cells in vitro, the organoid core facility has recently developed a method by which cells from primary tumors from patients can be grown in vitro. When samples are available for culture in vitro, we will test whether the cells derived from individual patients respond the same as the tumor in vivo in the same patient. For this experiment, cells in culture will be treated with the same drug (tamoxifen or fulvestrant) as the patient has received. We will conduct standard proliferation assays (MTT) assay over a range of doses of the drug as we are aware that intratumoral doses achieved clinically and doses in vitro can be quite different. If successful this analysis would validate the use of such organoid culture to predict patient response in the future. Therefore, we view this analysis as an opportunity to determine proof of principal of such technique and may have wide impact for several studies in the future.

Removal of Subjects

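### Each gene signature is tested only in the arm given the matching drug, so an association there could be read as drug-specific when the signature marks Ki67 change under either drug

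*Combined protocol and SAP*

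**What the plan says.** The Data Analysis part of the Statistical Analysis Plan states that "Presence of these gene signatures will be determined for all patients in this study". The next sentence sets the comparison: "Patients having signatures for responsiveness or resistance to tamoxifen (fulvestrant) will be compared with respect to change in Ki67 after treatment with tamoxifen (fulvestrant". The method named for it is a stratified ANCOVA. The parenthesis ties the tamoxifen signature to tamoxifen-treated women and the fulvestrant signature to fulvestrant-treated women.

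The only interaction in the plan concerns menopause: "Potential interaction will be tested for treatment by stratum (menopausal status". Nothing tests a signature in the other arm.

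Under Secondary Objectives the aim is put this way: "we will compare whether the same gene signature characterizes tumors that are resistant or sensitive to tamoxifen and fulvestrant respectively in patients samples".

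Two further passages bear on the point. For the primary analysis the outcome is "post treatment percentage of cells staining for Ki67 with covariate baseline percentage of cells staining for Ki67"; the signature sentence does not repeat the covariate. Under Laboratory Determinations and Pathology Review, and again under Correlatives/Special Studies, a portion of the surgical specimen is set aside for tumours over 1 cm, of which "half will be frozen for subsequent RNA extraction and expression profiling". The paragraph that follows takes RNA from paraffin sections and gives no time point.

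**The concern.** A contrast between signature groups inside one arm shows that the signature goes with Ki67 change on that drug. It cannot show that the link belongs to that drug. A general marker of endocrine response, or of Ki67 movement between core and excision whatever the treatment, gives the same positive result. Such movement occurs without active drug: the placebo group cited in the sample-size text fell by 7.1 points, with an SD of 18.0.

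The objective speaks of resistance or sensitivity to each drug respectively, and the trial as a whole is about choosing between the two. Randomisation offers the comparison that would help (does the tamoxifen signature behave differently on fulvestrant, and the reverse?), and the plan does not use it. What is at stake is the wording of a secondary conclusion, not the primary result.

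**Working it through.** **Inputs from the documents.** 29 evaluable per arm ("58 patients (29 patients in each study treatment arm) will be required"), a 15-point difference, two-sided 0.05, power 0.80, and cited SDs of 22.5 (fulvestrant 250 mg) and 18.0 (placebo).

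**Assumed, because the documents give no value.** Signature prevalence, size of the signature effect, and reliability of Ki67.

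**1. The plan's own figure.** Pooled SD = √[(22.5² + 18.0²)/2] = 20.37. Then n per arm = 2 × (20.37 × 2.802/15)² ≈ 29, or 58 in all, which matches. Pooling is an assumption, since the design SD is not stated. No power is given for the signature analysis.

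**2. Within-arm test when the effect is shared.** SE = SD × √(1/n₁ + 1/n₂).
- SD 18.0, 50% prevalence (14 vs 15): SE = 6.69, 15/6.69 = 2.24, power of the two-sample t-test 0.58.
- SD 22.5, 30% prevalence (9 vs 20): SE = 9.03, 15/9.03 = 1.66, power 0.36.

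Simulation over the same settings gives 35-59% for the tamoxifen arm. At least one of the two within-arm tests is significant in 58-83% (from the ends of the first range: 1 − 0.65² = 0.58 and 1 − 0.41² = 0.83). With an assumed 10-point shift the tamoxifen-arm figure is 20-30%; with 20 points it is 57-82%. The treatment-by-signature test rejects in about 5%, which is its nominal level when effects are equal. These are t-tests on change and do not adjust for baseline.

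**3. Planned type of analysis, with baseline Ki67 as covariate.** Simulation with 29 per arm, about 50% prevalence, assumed Ki67 SD 20 and true-change SD 8. The table gives the share of trials in which the tamoxifen-arm ANCOVA is significant for a signature with no drug specificity.

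| Signature marks | Reliability 1.0 | 0.8 | 0.6 |
|---|---|---|---|
| Pre-treatment proliferation only | 5% | 21% | 32% |
| Proliferation, read on the post-treatment specimen | 46% | 59% | 64% |
| A 15-point Ki67 difference common to both arms | 99% | 72% | 54% |

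The interaction test rejects in 4-6% in all nine settings. That does not hold once Ki67 is floored at zero. With an assumed baseline mean of 30 and SD of 15, and the plan's reductions of 5 and 20 points, the interaction's rejection rate for a pure pre-treatment proliferation marker can rise to about 10-18%.

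**4. Cost in precision.** The interaction is a difference of two within-arm contrasts, so its SE is √2 times larger. At SD 20.37 and 14 vs 15, the within-arm SE is 7.57 and the interaction SE is 10.71.
- Power for 15 points (normal approximation): Φ(15/7.57 − 1.96) = 0.51 within arm; Φ(15/10.71 − 1.96) = 0.29 for the interaction.
- Detectable at 80% power: 2.802 × 7.57 = 21.2 points within arm; 21.2 × √2 = 30.0 points for the interaction.
- Evaluable patients needed per arm for a 15-point interaction at 80% power: 8 × (20.37 × 2.802/15)² ≈ 116.

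Over SDs 18.0-22.5 and prevalence 30-50%, interaction power for 15 points is about 0.2-0.35.

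**The case against.** **The objective may be narrower.** The secondary endpoint asks whether the signatures are observed in these patients. The biomarker put forward for choosing fulvestrant is cyclin D1, not the signatures. A tumour that responds poorly to both drugs is still tamoxifen-resistant. This stands in part: nowhere does the plan claim that a signature selects between the drugs, and a reader should not infer that it does. The planned contrast does answer whether a signature goes with Ki67 change on its drug. It does not answer whether that link is particular to the drug, which is how the word respectively invites the result to be read.

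**Baseline adjustment removes pure proliferation markers.** A reader might infer that any signature marking proliferation would pass as a drug marker. The documents do not support that. With a pre-treatment signature, baseline Ki67 in the model and error-free measurement, the rate is the nominal 5%. Those conditions are not secured, however. The plan expects that "the cores will show considerable intratumoral heterogeneity in the extent of staining", it does not repeat the covariate for this analysis, and it freezes surgical tissue for RNA. Nor does adjustment separate a general response marker from a drug-specific one.

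**The 35-59% is not an error rate.** This is correct. It is the chance of detecting an association that truly exists in that arm. Only a drug-specific reading of it would be wrong.

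**The interaction has its own weaknesses.** This also stands. Power is low. A floor at zero can inflate its error rate. If RNA comes from the surgical specimen, the signature may itself be altered by the assigned drug, and randomisation then no longer protects the contrast. Frozen tissue is limited to tumours over 1 cm while eligibility starts at 5 mm, so a reading in every patient is not assured by that route.

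**Conclusion.** The point holds as a limit on interpretation. As written, the plan cannot tell a tamoxifen- or fulvestrant-specific signature from one that marks Ki67 change under either drug. Where Ki67 is measured with error or the signature is read after treatment, general proliferation is a further explanation.

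The size depends on assumptions. A 15-point effect shared by both arms, at 30-50% prevalence and the cited SDs, makes the tamoxifen-arm test significant in roughly 35-59% of trials. Prevalence, effect size and Ki67 reliability are not in the documents. The finding concerns one secondary correlative analysis; the primary comparison is untouched.

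**What to change.** For each signature, fit one ANCOVA in both arms together: post-treatment Ki67 on baseline Ki67, menopausal stratum, treatment, signature and treatment-by-signature.

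- Report the signature effect in each arm and the interaction, each with a confidence interval, and label the analysis exploratory.
- Check the scale or transformation because of the floor at zero.
- Read the signature for this analysis on paraffin sections of the pre-treatment core where available. State the time point, and reconcile the Data Analysis text with Laboratory Determinations and Pathology Review and with Correlatives/Special Studies.
- If only surgical-specimen RNA exists, report the result as descriptive.
- Describe a within-arm association alone as associated with Ki67 change on that drug. Do not treat a non-significant interaction as evidence against specificity.

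The cost is a few lines of SAP text and no additional patients. Using the core does depend on enough core tissue remaining. The downside is a wide interaction interval: at SD 20.37 and 50% prevalence the 95% half-width is about 1.96 × 10.71 = 21 points, so the claim becomes more modest.

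### The gene-signature analysis compares undefined responsive and resistant groups within one arm; a prespecified continuous score would use the same assay data more efficiently and remove the dependence on a cut-off

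*Combined protocol and SAP*

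**What the plan says.** The secondary objective, under Secondary Objectives and again in the endpoint lists, is worded as a question of presence: "Determine whether tamoxifen-resistance and fulvestrant-sensitivity gene expression signatures are observed in patients with cyclinD1 overexpressing breast cancers". The assay is described there and under Correlative Laboratory Research as "using selected gene by nanostring analysis by RNA extraction from paraffin embedded sections".

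The Data Analysis part of the Statistical Analysis Plan then takes two steps. First, "Presence of these gene signatures will be determined for all patients in this study". Second, "Patients having signatures for responsiveness or resistance to tamoxifen (fulvestrant) will be compared with respect to change in Ki67", and this is done "after treatment with tamoxifen (fulvestrant) by stratified ANCOVA". The tamoxifen signature is therefore examined in tamoxifen-treated women and the fulvestrant signature in fulvestrant-treated women. The predictor is a category in both cases.

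The signatures were established in cell lines. The text gives no gene weights, summary score, cut-off, classification rule or expected group sizes, and does not mention tumours that match neither signature or both. It gives no sample size or power for this comparison.

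Elsewhere the plan is more exact. Cyclin D1 has a full scoring rule with a positivity cut-off of 5, and the in vitro drug response is analysed by correlation and regression.

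**The concern.** Expression of selected genes is a set of measurements. Turning it into two classes has two consequences in a sample this small.

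- **Power.** Differences between tumours within a class are ignored. With 29 women and a 20/80 split, the smaller class holds about 6 (29 × 0.20 = 5.8), spread over two menopausal strata.
- **Dependence on an unwritten rule.** A cut-off must either be carried over from cell lines to RNA from paraffin-embedded tumours, where it need not apply, or be set on the trial's own patients. The trial is not blinded. A cut-off set with the Ki67 response in view would make the association look stronger than it is.

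At stake is whether this objective gives an interpretable answer about the signatures and Ki67 response. The treatment comparison is not at stake.

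**Working it through.** **Number of women.** "A total of 64 patients will be randomized in a 1:1 allocation (32 patients to the tamoxifen arm and 32 to the fulvestrant arm"). The plan requires 29 evaluable per arm for the primary comparison. That figure reproduces. The SD used is not stated, but the root mean square of the two quoted SDs is √[(18.0² + 22.5²)/2] = 20.37, and 2 × (1.960 + 0.842)² × 20.37² / 15² ≈ 29. A t-test calculation with SD 20 also gives 29. So 29 to 32 women per arm is the right range for a within-arm analysis, provided every tumour is assayed.

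**Assumptions, none of them in the documents.** The signature can be summarised as a score that is roughly normal and linearly related to Ki67 response, with a weak to moderate association.

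**Information kept when every tumour is assigned to one of two groups.** With share p in one group and φ the normal density at the cut, efficiency relative to the continuous score is φ(z_p)² / [p(1 − p)]. At the median this is 0.3989² / 0.25 = 0.637.

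| Split | Efficiency | Loss | 29 women act like | 32 women act like |
|---|---|---|---|---|
| 50/50 | 0.637 | 36.3% | 18.5 | 20.4 |
| 40/60 | 0.622 | 37.8% | 18.0 | 19.9 |
| 30/70 | 0.576 | 42.4% | 16.7 | 18.4 |
| 20/80 | 0.490 | 51.0% | 14.2 | 15.7 |

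**Information kept when two tails are compared and the middle is left out.** With share q in each tail, efficiency is 2φ(z_q)² / q.

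| Left out | Efficiency | Loss |
|---|---|---|
| 10% | 0.696 | 30.4% |
| 20% | 0.746 | 25.4% |
| 30% | 0.784 | 21.6% |
| 46% | 0.810 | 19.0% |
| 70% | 0.725 | 27.5% |
| 80% | 0.616 | 38.4% |

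**Power at n = 29, assumed partial correlation 0.5, two-sided 0.05.** By the Fisher z approximation with two covariates, power = Φ[atanh(r) × √(29 − 3 − 2) − 1.96], where r is multiplied by the square root of the efficiency for a split.

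- Continuous score: atanh(0.5) × √24 = 2.69, power 0.77.
- Median split: r = 0.5 × √0.637 = 0.399, giving 2.07, power 0.54.
- 25/75 split (efficiency 0.539): r = 0.367, giving 1.89, power 0.47.

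A simulation of the within-arm linear model (score or group, stratum, baseline; 8,000 runs) agrees:

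| n | Correlation | Continuous | Median split | 30/70 split | Outer thirds |
|---|---|---|---|---|---|
| 29 | 0.5 | 0.78 | 0.57 | 0.51 | 0.62 |
| 32 | 0.5 | 0.83 | 0.62 | 0.55 | 0.67 |
| 29 | 0.4 | 0.57 | 0.37 | 0.34 | 0.42 |
| 32 | 0.4 | 0.61 | 0.42 | 0.39 | 0.46 |

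The continuous score does best in every scenario tried. At a correlation of 0.4 it is itself underpowered.

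**The case against.** The objective asks whether the signatures are observed, and presence is a natural summary for that. A signature that separates responsive from resistant cells may have been built as a classifier, and the documents describe no ready-made score. If the tumours fall into two clearly distinct classes, grouping loses little. A continuous score also needs rules for normalisation and weighting, so prespecification is needed either way. The analysis is secondary and unpowered.

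All of this stands, and it limits the point. It does not supply the missing rule, and presence does not have to be the predictor in the Ki67 model merely because it answers the descriptive question.

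Three stronger readings are tempting, and the documents do not support them:

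- **That the plan throws away more than a third of the information.** That figure belongs to a normal, linearly related score with every tumour assigned. Leaving out a middle group usually brings the loss below a third.
- **That the plan excludes tumours matching neither signature.** It says presence is determined for all patients and states no exclusion. Their handling is undefined.
- **That unclassified tumours necessarily lower power further.** If they are the middle 30% of the score, the loss is about 22%, against 36% for a median split. Power falls below the median split (to about 0.39 at n = 29, correlation 0.5) if 30% are unclassified at random with respect to the score.

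**Conclusion.** The point holds as one of prespecification and efficiency. The plan makes a categorical, within-arm comparison on a quantitative assay, with no score, cut-off or rule for tumours outside the two groups. Under the stated assumptions the grouped analysis loses about 19% to 51% of the information across the main scenarios: 36% to 51% when all tumours are assigned, and typically 19% to 30% when a middle group is left out. At n = 29 and an assumed correlation of 0.5, that is power of about 0.77 against about 0.47 to 0.62. The range rests on normality, linearity and the assumed correlation. The risk of overstatement from a cut-off chosen with the Ki67 response in view does not depend on those assumptions. The primary comparison is unaffected.

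**What to change.** Before any Ki67 response is seen, add to the SAP:

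1. One continuous score per signature, built from the cell-line gene lists with fixed weights and normalisation; for example, mean standardised log expression of the resistance genes minus that of the sensitivity genes. The stopping rules look at Ki67 change in the first 10 and first 14 patients of an arm, so the score should be fixed before then, or by someone without access to those data.
2. The score as a linear term in the planned ANCOVA (baseline Ki67, stratified by menopausal status), within the arm given the matching drug and using every assayed tumour. Report the slope with its 95% confidence interval and a plot to check linearity.
3. Presence of the responsive or resistant signature as a descriptive table, with a stated rule for tumours that match neither or both. This still answers the objective as worded.

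The SAP should also reconcile determination in all patients with the tissue provision, "For tumors greater than 1 cm, a small portion of the surgical specimen not needed for diagnostics will be divided", half of which is frozen for RNA. Eligibility starts at 5 mm, and the same section also cites RNA from paraffin sections.

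**Cost.** A short SAP paragraph and the work of building the score. No extra patients, tissue or assays are needed. The analysis assumes approximate linearity, and the gain is small if the signature proves clearly bimodal.
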